10.2 ANALYSIS POPULATIONS

10.2.1 SAFETY POPULATION

The safety analysis population will contain all subjects for whom either the OMNI (canaloplasty alone), OMNI (canaloplasty AND trabeculotomy), or iStent inject is attempted. The attempt is defined as the OMNI instrument or iStent inject touching the study eyes even if the procedure is not completed. Subjects will be grouped according to their actual treatments.

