4.2 DEVICE DESCRIPTION

The OMNI Plus Surgical System "OMNI" is a single-handed, manually operated device designed to provide metered delivery of viscoelastic gel into Schlemm's canal and to cut trabecular meshwork tissue using a microcatheter. The device integrates an access cannula, a microcatheter, an internal fluid reservoir, and a simple catheter advancement and retraction wheel mechanism all into a single disposable handheld device.

Using only a single clear corneal incision to access the trabeculocanalicular aqueous outflow system, the OMNI Glaucoma Treatment System facilitates the transluminal viscodilation of all 360 degrees of Schlemm's canal and the cutting of up to all 360 degrees of trabecular meshwork from an ab interno approach. The system can be used with commercially available viscoelastics, such as Healon® PRO or Healon GV® PRO from Johnson & Johnson Vision, Amvisc® from Bausch & Lomb, or PROVISC® from Alcon. Viscoelastic fluid is not provided with the device.

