6.2 SAFETY ENDPOINTS

- Rates of ocular adverse events (AE) (intraoperative, postoperative)
- Reduction in best corrected distance visual acuity (BCDVA) from screening
- Secondary Ocular Surgical Interventions, including laser, for IOP control

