10.2.2 As TREATED

The Intent to Treat (ITT) analysis population will include all subjects randomized and grouped according to their randomization assignment (as randomized) regardless if they actually undergo the assigned procedure. The As Treated (AT) population consists of the subjects that actually undergo the assigned procedure and will be grouped according to their actual treatments. For this study, the AT population will be used for the primary analyses of the primary and other effectiveness endpoints. The effectiveness analyses may be performed for the ITT population if needed.

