10.5 SAFETY ANALYSIS

All safety analyses will be performed on the safety analysis population based on all available data by the three study groups separately.

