10.5.1 ADVERSE EVENT

AE will be classified as pretreatment, intraoperative, or postoperative. The number and the percent of eyes reporting at least 1 AE of a given type will be summarized.

Additionally, the number of reports of each type of AE will be provided.

Each AE will be summarized by incidence, percentage and the corresponding 95% confidence interval.

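### An eye whose operation is started but stopped before the device touches it falls outside the Safety population, so any intraoperative harm to it appears in no planned safety table (minor)

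*Combined protocol and SAP*

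**What the plan says.** - **Entry to the Safety population (10.2.1).** Entry requires an attempted procedure: "The attempt is defined as the OMNI instrument or iStent inject touching the study eyes even if the procedure is not completed". On grouping, the section adds: "Subjects will be grouped according to their actual treatments".
- **Use of that population (10.5).** "All safety analyses will be performed on the safety analysis population based on all available data by the three study groups separately". No second safety set or supplementary listing is named. The optional interim summary in 10.6 lists safety endpoints but names no population of its own.
- **Timing classes (10.5.1).** "AE will be classified as pretreatment, intraoperative, or postoperative".
- **As Treated population (10.2.2).** "The As Treated (AT) population consists of the subjects that actually undergo the assigned procedure".
- **Surgical access.** Section 4.2 says of OMNI: "Using only a single clear corneal incision to access the trabeculocanalicular aqueous outflow system". Section 3 describes iStent inject as also placed through one incision.
- **Collection.** The Surgical visit (8.4.3) captures surgical complications and intraoperative adverse events. Section 9 requires adverse events in the study eye during the trial to be documented whatever their relation to the device. The definition in 9.1 is narrower: it covers only subjects who have had treatment with the device.

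**The concern.** The study operation starts with the incision, but membership of the Safety population starts with device contact. Between the two lies a short interval in which an eye can be injured and the operation given up. Such an eye fails the 10.2.1 rule and drops out of every analysis in 10.5, although its complication has been collected.

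The stated objectives compare the safety of procedures, and the first safety endpoint in 6.2 expressly includes intraoperative ocular events. An operation stopped because of harm is therefore part of what the trial sets out to report. For rare surgical complications, the difference between no event and one event matters to a reader of the tables.

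**Working it through.** **Step 1. Apply the rules to each course of events.**

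| Course of the operation | Safety population (10.2.1) | In the 10.5 tables |
|---|---|---|
| Incision, harm, stopped with no device contact | No | No |
| Incision, harm, device then touches the eye, procedure not completed | Yes | Yes, by timing class (10.5.1) |
| Procedure completed | Yes | Yes |

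Only the first row is lost. Membership is decided per subject, not by when the event happened.

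**Step 2. Look for the first-row eye elsewhere.** It does not meet the As Treated definition. Section 10.3 would count it in the ITT demographics, history and accountability summaries, but none of these reports adverse events. Even if it were admitted to the Safety population, it would have no group, because grouping follows actual treatment and it received none.

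**Step 3. Check that redaction is not the cause.** The rules in 10.2.1, 10.2.2, 10.5 and 10.5.1 are readable. The blacked-out parts of section 10 concern sample size and effectiveness.

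**Step 4. Reproduce the denominator (5.1).** With 137 completers per group and 10% drop-out, 137 / 0.90 = 152.2, rounded up to 153; 3 × 153 = 459. This matches the plan.

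**Step 5. Illustrate the effect on one arm.** Assume k eyes of 153 are harmed and abandoned before contact, and that the arm has no other event of that type. As written, the table shows 0/(153 − k); with the eyes counted it shows k/153. Exact (Clopper-Pearson) 95% limits for x events in n are the 0.025 quantile of Beta(x, n − x + 1), or 0 when x = 0, and the 0.975 quantile of Beta(x + 1, n − x).

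| k | As written | With the eyes counted |
|---|---|---|
| 1 | 0/152 = 0% (0 to 2.40%) | 1/153 = 0.65% (0.02 to 3.59%) |
| 2 | 0/151 = 0% (0 to 2.41%) | 2/153 = 1.31% (0.16 to 4.64%) |
| 3 | 0/150 = 0% (0 to 2.43%) | 3/153 = 1.96% (0.41 to 5.62%) |

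**Step 6. How likely is any such eye?** The documents give no rate, so p is an assumption, and all 459 randomised subjects are taken to reach surgery. The expected number is 459p; the chance of at least one is 1 − (1 − p)^459.

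| Assumed p | Expected among 459 | Chance of at least one |
|---|---|---|
| 0.1% | 0.5 | 37% |
| 0.25% | 1.1 | 68% |
| 0.5% | 2.3 | 90% |
| 1% | 4.6 | 99% |

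**The case against.** Device contact is an explicit and coherent basis for a postmarket device study. It already takes in uncompleted procedures and agrees with the wording of 9.1. Early stops should be uncommon: eligibility requires a wide angle in all quadrants and previous uncomplicated cataract surgery, and surgeons are experienced with iStent inject and trained on OMNI. The eyes are not invisible either. Their complications are captured at surgery, serious events go to the sponsor under 9.3, and the ITT accountability table allows them to be identified. Finally, the interval precedes any device, and all arms are entered through an incision, so losses may well be similar across arms.

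Most of this stands, and it limits the consequence. It does not close the gap, because none of these routes puts the event into a table of adverse event rates. Balance across arms is plausible rather than assured. Randomisation takes place at Baseline, up to 14 days before surgery, and site staff know the assignment afterwards (5.2), so a decision to stop can be made knowing the arm. That is a reason to show the count by arm; it is not evidence of bias. The objection that exposure is a deliberate basis is met by keeping that set and adding a separate listing.

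**Conclusion.** The gap is definite but narrow: it concerns study-eye surgery that was started and then stopped with no device contact. It rests on reading 10.2.1 and 10.5 as written and needs no numerical assumption. Its size is unknown and probably small; one to three such eyes with events in an arm would move a reported 0% to between 0.65% and 1.96%. This is a matter of complete safety reporting, and its severity is minor.

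A reader might infer three stronger things that the documents do not support:

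- **That every eye harmed before device contact is lost.** It is not. An eye later touched by the device is included, and its event is classified and tabulated.
- **That a large share of intraoperative events is hidden.** Assuming that 0.5% to 2% of eyes are stopped early and that the event rate is 5% gives 0.8 to 3.1 of 7.7 eyes per arm, or 10% to 40%. Neither rate is in the documents. The calculation also counts every stopped eye as an event, whereas an operation given up for a poor view need not involve one.
- **That the comparison between arms is biased.** Nothing in the documents shows that early stops would differ by arm.

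**What to change.** 1. In 10.2.1, define the Safety population as all randomised subjects in whom study-eye surgery was started, from the first incision, whether or not a device touched the eye.
2. Add a grouping rule there: eyes with no device contact are shown under their randomised arm, with the number per arm in a footnote. All other eyes stay grouped by actual treatment.
3. Align the adverse event definition in 9.1 with the collection rule in section 9. Otherwise the added eyes could enter the denominators while their events fall outside the definition.
4. If the device-contact set is kept for the main tables, add a by-arm table or listing of adverse events in randomised eyes with surgery started and no device contact. Step 3 is still needed.

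The cost is a few sentences across 9.1 and 10.2.1, or one extra listing. No new assessment is needed, but the CRF should record whether surgery was started and whether a device touched the eye; the list in 8.4.3 names neither item. The downside is that a few eyes without device exposure enter the denominators, which the footnote makes visible.

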10.2.2 As TREATED

The Intent to Treat (ITT) analysis population will include all subjects randomized and grouped according to their randomization assignment (as randomized) regardless if they actually undergo the assigned procedure. The As Treated (AT) population consists of the subjects that actually undergo the assigned procedure and will be grouped according to their actual treatments. For this study, the AT population will be used for the primary analyses of the primary and other effectiveness endpoints. The effectiveness analyses may be performed for the ITT population if needed.

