5.3 STUDY DEVICE

The study device is the OMNI Plus Surgical System. Subjects randomized to one of the two OMNI treatment groups will undergo either ab-interno transluminal viscoelastic delivery for both hemispheres (360 degree treatment must be attempted) and trabeculotomy for one hemisphere (360 degree treatment must be attempted) (OMNI group), or to canaloplasty only (360 degree treatment must be attempted).

The Comparator group is:

- iStent inject (original or “W”)

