Below is a list of study procedures to be undertaken at the Baseline Visit which must take place no more than 14 days prior to surgery and only after satisfying the medication washout (Section 8.4.1. "Washout of Hypotensive Medications" and Table 2). Conduct ocular assessments in both eyes.

[figure not shown]
Subjects meeting all criteria at the Baseline Visit will be scheduled for surgery and be randomized to a treatment arm. Randomization to treatment group will be performed using a 1:1:1 ratio and will be stratified by site. Computer-generated randomization will be administered through the electronic data capture (EDC) system with separate block randomization (block of 6) sequences for each clinical site.

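### The two clauses defining the As Treated population, the primary effectiveness set, disagree on eyes that received another arm's procedure

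*Combined protocol and SAP*

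**What the plan says.** Section 10.2.2 sets out two populations. ITT is "all subjects randomized and grouped according to their randomization assignment (as randomized) regardless if they actually undergo the assigned procedure". The AT population "consists of the subjects that actually undergo the assigned procedure and will be grouped according to their actual treatments". The same section gives AT the leading role: "the AT population will be used for the primary analyses of the primary and other effectiveness endpoints". For ITT it says only: "The effectiveness analyses may be performed for the ITT population if needed". Sections 10.4.3 and 10.4.4 also run the covariate analysis and the other effectiveness endpoints on AT.

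The Safety population in 10.2.1 is built differently. It takes every subject in whom any of the three procedures was attempted, an attempt being contact of the instrument with the study eye, "even if the procedure is not completed. Subjects will be grouped according to their actual treatments". It does not require that the procedure be the assigned one.

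Assignment comes before surgery. Section 8.4.2 states: "Subjects meeting all criteria at the Baseline Visit will be scheduled for surgery and be randomized to a treatment arm". Section 8.4.3 allows up to 14 days between that visit and the operation. For the OMNI arms, section 5.3 says "360 degree treatment must be attempted". The synopsis describes the combined treatment as trabeculotomy of up to 360 degrees.

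**The concern.** The membership clause admits a subject only if the procedure performed was the procedure assigned. Within that set, actual and assigned treatment always agree, so grouping by actual treatment does nothing. That clause, like the name As Treated, has work to do only if subjects who received some other study procedure are members. The sentence therefore points to two memberships without choosing one.

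This matters because of where the sentence sits. It fixes the set for both confirmatory objectives, and no mandatory ITT result stands beside it. The literal membership reading removes technical failures from an arm after randomisation. The grouping reading moves them into another arm, which for a combined-arm eye given canaloplasty only means the non-inferiority contrast. Under section 5.2, site staff, sponsor clinical personnel and subjects all know the assignment once it is made, so an unsettled definition could be settled after results are known.

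**Working it through.** **Inputs from the documents.** Randomised: 153 per group, 459 in total. Completers: 137 per group, with 10% drop-out (synopsis, 5.1). Non-inferiority margin: 1.5 mmHg (section 2). Significance level: two-sided 0.025 per hypothesis (10.1).

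**The plan's own figure.** 137 / (1 − 0.10) = 152.2, rounded up to 153; 3 × 153 = 459. This reproduces. The 137 cannot be rebuilt because the power, SD and effect in 10.1 are redacted.

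**Step 1: classify each kind of eye under each clause.**

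| Eye | Membership clause governs | Grouping clause governs |
|---|---|---|
| Received the assigned procedure | Assigned arm | Same arm |
| Received no study procedure | Not in AT | Not in AT |
| Received another arm's procedure | Not in AT | Arm of the procedure received |
| Assigned procedure begun, not completed | 10.2.2 does not say | 10.2.2 does not say |

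The readings part on the third row. A switched eye leaves its assigned arm under both; they differ only on whether it enters the receiving arm. For a combined-arm eye given canaloplasty only, the combined arm is the same set either way and the canaloplasty-alone arm is not.

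**Step 2: size of the shift.** Let k combined-arm eyes receive canaloplasty only, and let their mean DIOP change differ from that of the canaloplasty-alone arm by d mmHg. Dropping them shifts that arm's mean by 0. Moving them in shifts it by k × d / (153 + k). The documents give neither k nor d. Assumed: 2%, 5% or 10% of 153 (k = 3, 8, 15) and d = 1, 2 or 4. Cells show mmHg and the percentage of the 1.5 mmHg margin.

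| k | d = 1 | d = 2 | d = 4 |
|---|---|---|---|
| 3 | 3/156 = 0.02 (1.3%) | 6/156 = 0.04 (2.6%) | 12/156 = 0.08 (5.1%) |
| 8 | 8/161 = 0.05 (3.3%) | 16/161 = 0.10 (6.6%) | 32/161 = 0.20 (13.3%) |
| 15 | 15/168 = 0.09 (6.0%) | 30/168 = 0.18 (11.9%) | 60/168 = 0.36 (23.8%) |

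On the 137 completers per arm, with k = 3, 7 or 14 and d from 1 to 3, the same formula gives 0.02 to 0.28 mmHg (1% to 19% of the margin).

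**Step 3: effect on the non-inferiority test.** Assumed: true difference 0, SD 4, one-sided level 0.0125 and normal approximation. Power = Φ((1.5 − shift)/SE − 2.241), where a positive shift means a worse canaloplasty-alone result.

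- Dropped: SE = 4 × √(1/137 + 1/137) = 0.483; power 0.81.
- 14 eyes moved, 2 mmHg better: shift = −28/151 = −0.185; SE = 4 × √(1/151 + 1/137) = 0.472; power 0.91.
- 14 eyes moved, 2 mmHg worse: shift = +0.185; same SE; power 0.71.

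For the same three cases, SD 3 gives 0.97, 0.99 and 0.93; SD 5 gives 0.60, 0.73 and 0.50.

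**The case against.** The strongest reply is that the sentence, read strictly, defines one set: subjects who underwent what they were assigned. The grouping clause is then redundant rather than contradictory. That is right as a matter of syntax. But a grouping clause and a population name that both lose all effect under the strict reading leave the intended set in doubt, and this is the primary analysis set.

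Other objections stand and limit the point:

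- A reader might infer that every eye not given its assigned procedure is dropped or moved. Eyes with no study procedure are outside AT under both readings.
- A reader might infer that the main example disturbs both objectives. It leaves the combined-arm set unchanged and bears only on Objective 2.
- A reader might infer that crossover is expected. No visible text says so. Sections 5.3 and 10.2.1 concern attempted and uncompleted procedures, and a partial trabeculotomy already falls within the synopsis description of the combined treatment. Conversion from iStent inject to OMNI is mentioned nowhere.
- The size is wholly assumed and its sign is unknown. The 24% figure needs 10% switching together with a 4 mmHg difference, which is 2.7 times the margin.
- Section 10.4.1 and part of 10.1 are redacted. Section 10.4.2 shows that 10.4.1 lists at least four criteria, and a rule for switched eyes could be among them. It would still leave 10.2.2, which is fully visible, needing correction.

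Section 10.7 requires deviations from the statistical plan to be noted. It gives little protection here, because adopting either reading could be presented as following the plan.

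**Conclusion.** The point holds in a limited form. The two clauses of the AT definition imply different sets, and an eye that received a different study procedure is either excluded or counted in another arm. For combined-arm eyes given canaloplasty only, the difference falls entirely on the canaloplasty-alone arm and the non-inferiority comparison. Under the assumed 2% to 10% switching and 1 to 4 mmHg difference, that arm's mean moves by about 0.02 to 0.36 mmHg, or 1% to 24% of the margin. At 2% switching and 2 mmHg it moves by 0.04 mmHg, which is negligible.

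The documents do not support saying that the plan has no handling rule anywhere, since relevant text is redacted, nor that the result is biased in a known direction. Whether ITT or AT should be primary is a separate question; the inconsistency remains wherever AT is used. The sponsor should correct it, but it does not by itself undermine the trial.

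**What to change.** Replace the AT sentence in 10.2.2 with one rule, set now and before any outcome data by arm are reviewed, including the optional interim summary in 10.6. Waiting until database lock would be too late in an open-label trial. Suggested content:

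- AT is all randomised subjects in whom a study procedure was attempted, with attempt defined as in 10.2.1.
- A subject in whom the assigned procedure was attempted stays in the assigned group, even if it was left incomplete or converted to another procedure.
- A subject in whom only another arm's procedure was attempted is grouped by that procedure and listed individually.
- Because both OMNI arms use one instrument, contact of the OMNI with the eye counts as an attempt at whichever OMNI procedure was assigned.

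If a set limited to subjects who received the complete assigned procedure is wanted, call it Per Protocol and use it as supportive. Check any rule in the redacted parts of 10.1 and 10.4.1 against the new sentence.

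The cost is a short text change, with no new data or subjects. The analysis set becomes slightly larger and less selected, because technical failures stay in the arm to which they were randomised.

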
(Ocular criteria apply to the study eye only unless otherwise stated)
	
 Implanted with a MIGS or other glaucoma device [REDACTED] Trabeculectomy or other bleb forming procedure [REDACTED] Prior canaloplasty, goniotomy, or trabeculotomy including procedures [REDACTED] Ciliary ablation procedures including Endocyclophotocoagulation (ECP), Cyclophotocoagulation (G probe), Micropulse laser, or high intensity focused ultrasound (HIFU) [REDACTED] 
2. Any other form of glaucoma other than OAG
 
3. Use of topical ocular steroids that cannot be stopped [REDACTED]
 
4. In the Investigator's judgement, predisposed to significant risk because of washout of ocular hypotensive medications.
 
5. Concurrent ocular pathology or systemic medical condition which, in the Investigator's judgment, would either place the subject at increased risk of complications, contraindicate surgery, place the subject at risk of significant vision loss during the study period (e.g., wet AMD, corneal edema, Fuch's dystrophy, active intraocular infection or inflammation within 30 days prior to Screening Visit, etc.), or interfere with compliance to elements of the study protocol (e.g., returning to investigator's office for follow-up visits).
 
6. History of penetrating keratoplasty or other corneal transplant; corneal abnormality that would prevent reliable IOP measurement (e.g. keratoconus, abnormally thick [$\geq 600 \mu\text{M}$] or thin [$\leq 500 \mu\text{M}$] cornea based on optical or ultrasound pachymetry of central corneal thickness [CCT])

--	---

	
7. BCDVA of 6/60 (20/200) or worse in the fellow eye not due to cataract
 
8. Participation of the study eye in any other ocular interventional study ≤ 30 days prior to Baseline visit and throughout this study
 
9. Women of childbearing potential if they are currently pregnant or intend to become pregnant during the study period; are breast-feeding; or are not in agreement to use adequate birth control methods to prevent pregnancy throughout the study.

Number of Subjects Enrolled and Treated	459 (153 per treatment group) to complete 411 (137 per group) at 12 months postoperative assuming a 10% drop-out rate
Number of Sites	A minimum of 24 and up to 26 sites in the European Union, United Kingdom, and/or Switzerland

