5.2 METHODS USED TO MINIMIZE BIAS

This study is randomized using block (a block of 6) randomization and neither the Investigator, the investigative site staff, or Sponsor clinical personnel will have knowledge of or access to the randomization scheme. Randomization to treatment group will be performed using a 1:1:1 ratio and will be stratified by site. Treatment allocation bias will thus be avoided. Once randomized into the study, the Investigator, the investigative site staff, Sponsor clinical personnel and the subject will be unmasked to the treatment assignment for each subject.

The study is multicenter with sites in at least 5 countries. The potential bias inherent in single-center trials is thus eliminated. Moreover, no site can randomize more than 25% of the study subjects. The location of sites in multiple countries incorporates greater diversity in the patient population as well as subtle geographic differences in treatment norms/standard of care allowing greater generalizability of the study results.

Mean diurnal IOP is the basis for the primary endpoint. DIOP averages three separate IOP measurements taken at different times of day. This mitigates the risk of a single measurement being unusually high or low and subsequent regression to the mean. IOP measurements will be taken using Goldmann applanation tonometry with routine and documented calibration required. IOP will be measured by 2 different study personnel (an operator and a recorder) closely following the procedure used in AGIS.¹⁹ This technique prevents unintentional bias on the part of the Investigator or technician measuring and recording the IOP.

Reintroduction and discontinuation of ocular hypotensive medications will follow a protocol defined procedure to ensure standardization across sites and remove the potential for bias in treatment regimen.

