8.4.3 SURGICAL VISIT

The Surgical visit must occur no more than 45 days after the Screening visit and no more than 14 days after the Baseline visit.

Study investigators will be experienced with iStent inject implantation and will have received training on the OMNI Surgical System prior to site activation. Surgery will take place after the subject successfully completes all screening and baseline assessments and is confirmed eligible to participate in the study per inclusion / exclusion requirements.

Surgeons should follow their standard peri-operative medication regimen.

The following information will be captured at this visit:

- Surgical complications
- Number of iStent inject stents implanted (1, or 2), implantation attempts, number of injectors used, any difficulties with implantation
- Intraoperative AEs
- Perioperative medications (topical hypotensive medications administered)

8.4.4 DAY 1

1. Document changes in ocular hypotensive medications.
2. Measure IOP with Goldmann tonometer is recommended between 8:00 am and 10:00 am. Refer to Appendix A, Section 19.1.3.
3. Conduct slit lamp examination. Refer to Appendix A, Section 19.1.4 for gradingscales.
4. Record any ocular AE.
5. Schedule the subject to return for the Week 1 Visit between the recommended time frame of 8:00 am and 10:00 am.

8.4.5 WEEK 1 (DAYS 5 TO 9), MONTH 1 (DAYS 21 TO 35), MONTH 3, (DAYS 70 TO 98), MONTH 6 (DAYS 150 TO 210)

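### The superiority test should use the ITT set as primary: As Treated membership is settled after the arm is known, ITT is optional in the visible text, and the As Treated definition is inconsistent

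*Combined protocol and SAP*

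**What the plan says.** Section 10.2.2 defines two effectiveness sets. ITT is everyone randomised, grouped as randomised. The second set is defined thus: "The As Treated (AT) population consists of the subjects that actually undergo the assigned procedure and will be grouped according to their actual treatments". As Treated is then made primary: "For this study, the AT population will be used for the primary analyses of the primary and other effectiveness endpoints". No distinction is drawn between Objective 1 (superiority of OMNI canaloplasty plus trabeculotomy over iStent inject) and Objective 2 (non-inferiority of canaloplasty alone, margin 1.5 mmHg). On ITT the section says only: "The effectiveness analyses may be performed for the ITT population if needed". Section 10.3 commits to ITT for demographic, baseline, history and accountability tables. Section 10.4.3 uses As Treated for the covariate analysis.

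On timing, section 8.4.2 says: "Subjects meeting all criteria at the Baseline Visit will be scheduled for surgery and be randomized to a treatment arm". Section 8.4.3 says: "The Surgical visit must occur no more than 45 days after the Screening visit and no more than 14 days after the Baseline visit". On masking, section 5.2 says: "Once randomized into the study, the Investigator, the investigative site staff, Sponsor clinical personnel and the subject will be unmasked to the treatment assignment".

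On numbers, the synopsis row for subjects enrolled and treated reads: "459 (153 per treatment group) to complete 411 (137 per group) at 12 months postoperative assuming a 10% drop-out rate". Section 5.1 gives the same 459 as the number to be randomised.

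Sections 10.4.1 and 10.4.5 and part of 10.4.2 are redacted.

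**The concern.** A superiority test is protected by randomisation when subjects are compared in the groups to which they were allocated. Here the primary set is formed later. A subject can be randomised, learn the arm, and not have the assigned operation. That subject then leaves the primary comparison, or on the other reading of the definition moves to another arm. If this happens for reasons linked to both arm and prognosis, the contrast is biased and the 0.025 level may not hold. Because ITT is optional, the decision to run it could be taken after results are known.

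The definition adds a separate problem. If every As Treated subject had the assigned procedure, grouping by actual treatment changes nothing. If the grouping clause is meant to do something, membership is not as stated. A crossover could therefore be dropped or regrouped. A combined-arm eye whose trabeculotomy is fully abandoned could be dropped, kept, or moved to canaloplasty alone, which is the Objective 2 arm. The synopsis and section 5.3 deal with partial treatment but not with this case. Section 10.2.1 defines an attempted procedure for the safety set; section 10.2.2 does not say whether an attempt is enough for As Treated.

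**Working it through.** **The plan's own figures.** 137 / 0.90 = 152.2, so 153 per group; 3 x 153 = 459; 3 x 137 = 411; 0.025 + 0.025 = 0.05. All reproduce. Section 5.1 applies the 10% to the 12-month follow-up, so there is no visible allowance for subjects randomised but never operated on.

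The 137 cannot be traced to its inputs because effect, SD and power are redacted. A two-sample t calculation for 1.5 mmHg at two-sided 0.025 gives 136.4, so 137, both with SD 4.0 and 80% power and with SD 3.5 and 90% power. Everything below therefore rests on assumed inputs.

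**Step 1: possible error under As Treated.** Let a share f of the combined arm leave the set, let those eyes do d mmHg worse than the eyes that stay, and let iStent inject losses be k times as frequent with the same d. Then

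- bias = f x d x (1 - k)
- SE = SD x sqrt(2/137), which is 0.483 at SD 4.0
- one-sided error = 1 - Φ(2.2414 - bias/SE), where 2.2414 is the critical value for 0.0125

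| f | d (mmHg) | bias, k = 0 | error, k = 0 | bias, k = 0.5 | error, k = 0.5 |
|---|---|---|---|---|---|
| 3% | 3 | 0.09 | 0.020 | 0.045 | 0.016 |
| 3% | 5 | 0.15 | 0.027 | 0.075 | 0.019 |
| 10% | 3 | 0.30 | 0.053 | 0.15 | 0.027 |
| 10% | 5 | 0.50 | 0.114 | 0.25 | 0.042 |

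With k = 0 the range is 0.021-0.145 at SD 3.5 and 0.018-0.079 at SD 5.0. With k = 1 the bias is zero and the error stays at 0.0125.

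**Step 2: does ITT with zero change for unoperated subjects cure this?** Not in general. Suppose 10% go unoperated in the iStent inject arm only, the mean reduction is 7 mmHg in both arms, SD is 4.0, and 10% of operated subjects drop out at random and are left out.

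- iStent inject: 153 x 0.9 x 0.9 = 123.9 operated with data, plus 15.3 unoperated, makes 139.2 analysed; operated share p = 0.890.
- OMNI: 153 x 0.9 = 137.7 analysed.
- No prognosis link: iStent inject mean = 0.890 x 7 = 6.23, a spurious difference of 0.77. Variance = 16p + p(1 - p) x 49 = 19.0. SE = sqrt(16/137.7 + 19.0/139.2) = 0.503. Error = 1 - Φ(2.2414 - 1.53) = 0.24.
- Unoperated eyes 5 mmHg better: operated mean = 7 - 0.10 x 5 = 6.5; arm mean = 0.890 x 6.5 = 5.79; difference 1.21; SE 0.498; error 0.58.
- As Treated in that last case: bias 0.50; SE = 4 x sqrt(1/137.7 + 1/123.9) = 0.495; error 0.11. In simulation, requiring both sets gave the same error as As Treated alone.

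**Step 3: power cost of ITT with zero change.** Assume a true difference of 1.5, SD 4.0, iStent inject mean reduction 5 or 7, the same unoperated share in both arms, and the same random dropout. Each arm's variance is 16p + p(1 - p) x (its operated mean)².

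| Unoperated, both arms | As Treated power | ITT difference (1.5p) | ITT SE | ITT power |
|---|---|---|---|---|
| 3% | 0.79 | 1.450 | 0.489-0.502 | 0.74-0.76 |
| 10% | 0.76 | 1.335 | 0.502-0.538 | 0.59-0.66 |

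**The case against.** The strongest reply is that nothing shows the two sets will differ. Allocation is concealed and stratified by site. Fourteen days is a maximum. Subjects must already be scheduled for canal-based surgery. Full-circumference treatment need only be attempted, so a difficult OMNI case need not leave the set. The accountability tables in section 10.3 cover both sets, so any divergence would be visible. All of this stands. It lowers the likely size of the problem but does not change which set is primary.

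A reader might infer from section 8.4.3 ("Study investigators will be experienced with iStent inject implantation and will have received training on the OMNI Surgical System prior to site activation") that OMNI procedures will fail more often. The documents do not support that: section 5.4 also selects surgeons for experience with other minimally invasive glaucoma surgery, and no failure rate is given.

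Redaction also limits the point. Section 10.4.2 shows that section 10.4.1 lists at least four criteria bearing on absent 12-month values, and these may cover surgery not performed. Section 10.4.5 may hold an ITT analysis. The absence of a criterion for ITT is therefore a statement about the visible text only. Section 10.2.2 itself is unredacted and makes As Treated primary.

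Finally, ITT needs a rule for unoperated subjects, and the choice of target quantity is the sponsor's. The errors in step 2 are measured against a null in which everyone is operated on, which zero-change ITT does not target. That is a good argument against a single imputation, but not for leaving ITT optional.

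**Conclusion.** The point holds as an inexpensive improvement that should be made. The wording facts are certain: As Treated is primary for superiority, ITT is optional in the visible text, the arm is known before surgery, and the As Treated sentence is inconsistent.

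The size of any bias is not known, nor is its direction. The 0.020-0.114 range needs losses in the combined arm only, and its top end needs 10% lost with a 5 mmHg deficit. The documents give no expected number of unoperated or crossover subjects.

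Two stronger readings should be resisted. One is that randomisation gives the superiority contrast no protection, or that its level is in fact inflated. With full completion, or losses balanced by prognosis, there is no bias. The other is that ITT with zero change, or ITT plus As Treated agreement, settles the matter. Step 2 shows that neither protects against every arm-specific pattern.

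**What to change.** Amend section 10.2.2, and 10.4.2 for item 5, before outcome data are reviewed:

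1. Make ITT, as already defined, the primary set for Objective 1, with As Treated supportive.
2. Make the ITT effectiveness analysis mandatory in place of the present optional sentence.
3. For Objective 2, report ITT and As Treated, and claim non-inferiority only if both meet the 1.5 mmHg margin.
4. State one As Treated membership and grouping rule that covers crossovers and a combined-arm eye whose trabeculotomy is fully abandoned.
5. Include randomised but unoperated subjects in the tipping-point analysis, varying their values separately by arm and consistently with the rules in section 10.4.1. For superiority, do not rely on a single zero-change imputation or on a condition that As Treated must agree.

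Cost: the sample size does not change, and ITT baseline and accountability tables are already planned. If everyone receives the assigned procedure, the sets coincide and the cost is nil. Otherwise some power is lost, depending on how unoperated subjects are handled (step 3 gives the zero-change case), and the estimate may be less favourable.
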